### 1.2.2.3 Other Secondary Endpoints

#### 1.2.2.3.1 Efficacy Endpoint

- Stability of response defined as the proportion of participants able to achieve stable platelet response, which is defined as no 2 scheduled visits, at least 4 weeks apart, with a platelet count less than 50,000/ $\mu$ L, without an intervening visit with a platelet count  $\geq$ 50,000/ $\mu$ L, within a period of 24 weeks following initial achievement of the platelet response (initial platelet response defined as platelet count  $\geq$ 50,000/ $\mu$ L within 12 weeks of initiation of treatment with rilzabrutinib during the study).

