**Table 3 - Populations for analyses**

Population	Description
Screened	All participants who signed the informed consent form (ICF).
Randomized	All participants from screened population who have been allocated to a randomized intervention by IRT regardless of whether the intervention was received or not.
Intent-to-treat (ITT)	All randomized participants. Participants will be analyzed according to the intervention allocated by randomization.
Modified ITT (mITT)	All participants from ITT population who are exposed. Participants will be analyzed according to the intervention allocated by randomization.
Population without trial impact (disruption) due to COVID-19	All randomized participants without any major deviation related to Covid-19.
Safety	All randomized participants who take at least 1 dose of study intervention, regardless of the amount of treatment administrated. Participants will be analyzed according to the intervention they actually received (ie, "as-treated" defined below).
Pharmacokinetic (PK)	All randomized and exposed participants (safety population) with at least one post-baseline PK sample. Participants will be analyzed according to the intervention they actually received.
Open-Label (OL)	All participants who are exposed to active intervention (ie, rilzabrutinib) during the open-label period (ie, between the first OL visit at the nominal protocol visit Week 25 and the first LTE visit at the nominal protocol visit Week 53).
Long-term-extension (LTE)	All participants who are exposed to active intervention (ie, rilzabrutinib) during the LTE period (ie, on or after the first LTE visit at the nominal protocol visit Week 53).
Rilzabrutinib safety	All randomized participants who take at least 1 dose of the active intervention (ie, rilzabrutinib) during the study (ie, exposed to rilzabrutinib in the safety population during double-blind, open-label or LTE period).

Participants exposed to study intervention before or without being randomized will not be considered randomized and will not be included in any analysis population. The safety experience of these participants will be reported separately.

Randomized participants for whom it is unclear whether they took the study intervention will be considered as exposed and will be included in the safety population as randomized.

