### 3.3.2 Supportive secondary endpoint(s)

#### 3.3.2.1 *Other secondary endpoint – Stability of platelet response*

To qualify for a stable platelet responder (see endpoint definition in [Section 1.2.2.3.1](#)), a participant must have met ALL of the following criteria:

- Achieving initial platelet response, ie, platelet count  $\geq 50,000/\mu\text{L}$  within 12 weeks of initiation of rilzabrutinib [during double-blind period (protocol visit Week 2 to Week 13) for participants randomized to rilzabrutinib group, or during open-label period (protocol visit Week 26 to Week 37) for participants randomized to placebo group], and
- Following the initial platelet response, achieving platelet count  $\geq 50,000/\mu\text{L}$  for a period of 24 weeks, where
- There would be no 2 scheduled visits, at least 4 weeks apart, with a platelet count less than  $50,000/\mu\text{L}$ , without an intervening visit of platelet count  $\geq 50,000/\mu\text{L}$ . In other words, a participant would not be qualified for a stable responder if the participant has consecutive platelet counts  $< 50,000/\mu\text{L}$  for 4 weeks or longer (ie, from the first to the last occurrence of  $< 50,000/\mu\text{L}$  without any intervening visit of platelet count  $\geq 50,000/\mu\text{L}$ ) during this 24 weeks period after the initial response has been achieved. The participant's platelet counts within 4 weeks of rescue regimen will be considered as no response.
- Missing platelet count will be considered as no response.

The proportion of stable response will be calculated along with its 95% confidence interval (via normal approximation) in the open-label population ([Section 2](#)) as well as by randomized treatment group at the beginning of double-blind treatment, respectively.

For participants who are identified as a stable platelet responder, the duration of response will be descriptively summarized in the rilzabrutinib safety population ([Section 2](#)) as well as by randomized treatment group at the beginning of double-blind treatment, respectively. The duration of stable platelet response defined above is from the start date of stable platelet response up to

- The date of the first occurrence of 2 or more consecutive platelet counts  $< 50,000/\mu\text{L}$  for 4 weeks or longer (ie, when the stable response is lost), or
- 12 months after entering LTE,

whichever earlier.

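### The stable-response proportion is taken over the open-label population, which omits rilzabrutinib-arm participants who never enter open label and biases the figure upward

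*SAP*

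**What the plan says.** SAP 1.2.2.3.1 defines stability of response from a first platelet count of at least 50,000/μL that occurs "within 12 weeks of initiation of treatment with rilzabrutinib during the study". It then requires that, over the next 24 weeks, no two scheduled visits at least 4 weeks apart fall below that level without a qualifying visit between them.

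SAP 3.3.2.1 makes this operational. The initial response is looked for "during double-blind period (protocol visit Week 2 to Week 13) for participants randomized to rilzabrutinib group", and in the open-label period for those randomized to placebo. On missing data it says: "Missing platelet count will be considered as no response".

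On the population, the same section says: "The proportion of stable response will be calculated along with its 95% confidence interval (via normal approximation) in the open-label population", and the sentence continues "as well as by randomized treatment group at the beginning of double-blind treatment, respectively". Table 3 defines the open-label population as "All participants who are exposed to active intervention (ie, rilzabrutinib) during the open-label period".

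Protocol section 4 allows two exits without open-label treatment. Participants judged non-responders at Week 12 may leave the study instead of entering open label. Participants who stop blinded treatment between Weeks 13 and 24 may decline open label.

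**The concern.** For the rilzabrutinib arm, time zero is double-blind Day 1, but membership of the denominator is decided later, at open-label entry. A participant who starts rilzabrutinib, stops in the double-blind period and does not go on to open label has begun the drug and has almost no way of meeting the 24-week rule. The missing-data rule would make that participant a failure, but the choice of population removes the participant before the rule can apply.

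What is at stake is the meaning of the reported figure. A reader will take it as the chance that someone who starts rilzabrutinib reaches a stable response. As written, it is that chance among those who stayed long enough, and chose, to take open-label drug.

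**Working it through.** The plan gives no figure for this endpoint, so there is none to reproduce. The check has two parts: which excluded participants could have been stable, and how far their removal moves the proportion.

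**Inputs.** The initial-response window for the rilzabrutinib arm is Weeks 2 to 13, the stability window is 24 weeks, the failure span is 4 weeks or more, and missing counts as no response (SAP 3.3.2.1). Platelet counts are weekly, and Week 25 is the last double-blind visit (protocol Tables 1 and 2). The planned adult arms are 129 and 65 (SAP section 4). The share who never enter open label is not stated; 5% and 10% are assumptions.

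**Step 1: who can still qualify.** Let the first response be at Week k and the last available count, at or above the threshold, at Week s. Later visits are missing and count as no response.

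- The missing run goes from Week s + 1 to Week k + 24, a span of (k + 24) − (s + 1) = k + 23 − s weeks.
- Stability requires that span to be under 4 weeks, so s ≥ k + 20.
- For k = 2, s must be at least 22. For k = 5, s must be at least 25. For k = 6, s must be at least 26, which is beyond the double-blind period.

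Nobody whose counts end before Week 22 can therefore be stable. The only excluded participants who can be stable had a first response by Week 5, had adequate counts to Weeks 22–25 (depending on k), and then declined open label.

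**Step 2: effect on the proportion.** Let N be the rilzabrutinib starters, D those who never enter open label, x the stable responders among all starters, and e the stable responders among the D excluded.

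- Proportion among all starters: x/N.
- Proportion in the open-label population: (x − e)/(N − D).
- Ratio of the second to the first: [(x − e)/x] × [N/(N − D)], which is at most 1/(1 − d) with d = D/N.

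The bound is reached when e = 0. The ratio exceeds 1 whenever e/D is below x/N, that is, when stable response is rarer among those excluded than among all starters. Step 1 makes that all but certain.

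**Step 3: size.** SAP section 4 assumes 25% for the primary endpoint. That is a different endpoint, and 25% is borrowed here only as a convenient value.

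| d | Among all starters | Open-label figure, at most |
|---|---|---|
| 5% | 25% | 0.25/0.95 = 26.3% |
| 10% | 25% | 0.25/0.90 = 27.8% |

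In whole participants, suppose 13 of the 129 in the rilzabrutinib arm (10.1%) do not enter open label and e = 0. Then 26/129 = 20.2% becomes 26/116 = 22.4%, and 32/129 = 24.8% becomes 32/116 = 27.6%.

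Pooling with placebo switchers dilutes the effect, since none of them is lost. With 50 switchers and a common rate of 20%, the pooled figure is 0.20 × 179/166 = 21.6%. With 60 it is 0.20 × 189/176 = 21.5%.

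**The case against.** The strongest reply is that the sentence describes two presentations, and that the one by randomized group names no population. SAP 3.1 makes ITT the default for secondary efficacy unless otherwise specified, so the by-arm figure could be read as covering everyone randomized, with missing counts as no response. That would give the right denominator in the rilzabrutinib arm. This stands as a possible reading but not as a cure. The more natural reading is a split of the open-label population just named. An ITT reading would also count placebo participants who never took rilzabrutinib as failures of a rilzabrutinib endpoint. Under either reading the open-label figure itself is unchanged.

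It is also fair to say that the loss may be small. Protocol section 4 offers open label both to Week 12 non-responders and to those who stop blinded treatment for safety or other reasons. Those who accept stay in the denominator as failures. The high treatment discontinuation that SAP 3.3.1.2.3 expects concerns the blinded period and is not an estimate of d.

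Several stronger inferences are tempting, but the documents do not support them:

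- **Every stable responder must be in the open-label population.** Step 1 shows the exception, which is why 1/(1 − d) is an upper bound and not the exact factor.
- **A d of 25% is plausible.** If all 65 placebo participants switched, 0.25 × (129 + 65) is about 48 of the 129 rilzabrutinib participants never entering open label. Nothing in the documents points to that.
- **The section contradicts itself because "the duration of response will be descriptively summarized in the rilzabrutinib safety population".** That summary covers only participants already classed as stable responders, so it implies no competing denominator.
- **A treatment comparison is distorted.** No between-arm contrast is planned for this endpoint.

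**Conclusion.** The point holds. As written, the open-label figure for stable response is biased upward because it conditions on open-label entry, an event after the clock has started in the rilzabrutinib arm. The bias is at most a factor of 1/(1 − d). At a 25% rate among all starters that is up to 1.3 percentage points at d = 5% and up to 2.8 at d = 10%.

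The direction rests on the SAP's own visit schedule and missing-data rule, and on the narrow exception in Step 1 being rare. The size rests on assumed values, because neither the stable-response rate nor d is stated.

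The endpoint is a supportive one, with a proportion and an interval but no test, and it is outside the fixed sequence in SAP 3.5. Type I error and the primary conclusion are not affected. A reader might extend the point to the normal-approximation interval, but that is a separate matter of preference and no part of this conclusion.

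**What to change.** In SAP 3.3.2.1, calculate the proportion in the rilzabrutinib safety population, which Table 3 already defines as "All randomized participants who take at least 1 dose of the active intervention (ie, rilzabrutinib) during the study". Present it overall and by randomized group, and name that denominator for both. State that participants without enough follow-up to meet the 24-week rule count as not stable. The open-label figure may be kept as supportive.

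This suits both arms: placebo participants enter the denominator when they first take rilzabrutinib, so in practice only the rilzabrutinib arm changes. It also brings back the rare early responder who declines open label.

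The cost is a change of wording in one section, with no new data collection. The downside is a slightly less favourable figure.

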### 3.3.2.2 Other secondary endpoint – QOL endpoints

ITP-PAQ transformed score by scale (domain) and its change from baseline will be descriptively described for adult participants (see details in [Section 3.7.3.2](#)).

ITP-KIT summary score and its change from baseline will be descriptively described for pediatric participants (see details in [Section 3.7.3.3](#)).

## 3.4 TERTIARY/EXPLORATORY ENDPOINT(S) ANALYSIS

### 3.4.1 Definition of endpoint(s)

Please see [Section 1.2.2.4.1](#) and [Section 1.2.2.4.2](#).

Additional details are provided for specific exploratory efficacy endpoints below. Details of COA related endpoints could be found in [Section 3.7.3](#).

*Proportion of participants able to achieve platelet counts  $\geq 50,000/\mu\text{L}$  for 4 out of last 8 weeks of the 24-week treatment period*

Refer to [Section 3.2.1](#).

*Percentage of weeks with platelet count  $\geq 50,000/\mu\text{L}$  OR between  $\geq 30,000/\mu\text{L}$  and  $< 50,000/\mu\text{L}$  and at least doubled from baseline over the 24-week blinded treatment period in the absence of rescue therapy*

Refer to [Section 3.3.1.1](#). For each participant, percentage will be based on the available number of weeks with platelet counts including the weeks censored due to rescue therapy during the double-blind period.

*Proportion of participants with complete response (defined as platelet count  $\geq 100,000/\mu\text{L}$  on 2 consecutive visits at least 5 days apart and no bleeding or rescue ITP therapy use on and through these two visits.*

To qualify for a complete responder, a participant must have met ALL of the following criteria:

- Platelet counts  $\geq 100,000/\mu\text{L}$  on 2 consecutive visits at least 5 days apart, any time from Week 2 to Week 25 and
- No bleeding on and through these two visits (ie, bleeding events identified by SMQ = Haemorrhages via broad and narrow search in eCRF “Adverse Events”);
- Not rescued within the 4 weeks prior to the elevated platelet count and on and through these two visits.

*Proportion of participants with platelet count  $\geq 50,000/\mu\text{L}$  on 2 consecutive visits at least 5 days apart and no rescue ITP therapy use on and through these two visits.*

To qualify for a responder, a participant must have met ALL of the following criteria:

- Platelet counts  $\geq 50,000/\mu\text{L}$  on 2 consecutive visits at least 5 days apart, any time from Week 2 to Week 25 and

- Not rescued within the 4 weeks prior to the elevated platelet count ([Section 3.3.1.1](#)) and on and through these two visits.

*Proportion of participants who have a platelet count that exceeds 250,000/ $\mu$ L or 450,000/ $\mu$ L (for participants on TPO-RA)*

To qualify for a responder, a participant must have met ALL of the following criteria:

- Concomitantly on TPO-RA;
- Platelet counts  $>250,000/\mu\text{L}$  (or  $>450,000/\mu\text{L}$  respectively) any time from Week 2 to Week 25 and
- Not rescued within the 4 weeks prior to the elevated platelet count ([Section 3.3.1.1](#)).

*Percent change from baseline on CS dose / TPO-RA dose*

Percent of dose change will be calculated at Week 53 (ie, Study day 365  $\pm$  3 days) and after 12 months on the LTE period (ie, Study day 701 ie, Study day 365  $\pm$  14 days).

*Proportion of participants who switch to rilzabrutinib as a monotherapy during the first year of the LTE period*

To qualify for “switching to rilzabrutinib as a monotherapy”, a participant must have stopped the concomitant ITP medication permanently during the first year of the LTE period (ie, from 1st dose during LTE up to Study day 701  $\pm$  7 days).

*Proportion of participants who decrease their CS dose  $>50\%$  relative to baseline values during the first year of the LTE*

Qualified participants are those who have CS dose decrease by  $>50\%$  from baseline during the first year of the LTE period (ie, from 1st dose during LTE up to Study day 701  $\pm$  7 days).

*Proportion of participants who manage to reduce their dose or stop TPO-RA agonists during the first year of the LTE*

Qualified participants are those who have TPO-RA agonist dose decreased or stopped during the first year of the LTE period (ie, from 1st dose during LTE up to Study day 701  $\pm$  7 days).

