2. BACKGROUND

2.1. Overview of Immune Thrombocytopenia (ITP)

Immune Thrombocytopenia (ITP) is characterized by autoantibody-mediated destruction of platelets and impaired platelet production, which result in thrombocytopenia and a predisposition to bleeding associated with morbidity and mortality.

In general, pharmacotherapy (corticosteroids [CSs], intravenous immunoglobulin [IVIg] or anti-D) is used for symptomatic participants with low platelet counts for reducing platelet destruction. While a majority of participants respond initially to CSs, the rate of continued remission is low. Second line therapies include rituximab and splenectomy and are associated with risk of sepsis and immune suppression. Thrombopoietin (TPO) mimetics ([Bussel 2007](#)) are approved for the treatment of participants with chronic ITP who have not had sufficient responses to CSs, IVIg, or splenectomy. Second-line treatment with TPO-RAs have a clinical response rate of 80%, however approximately one-third of participants discontinue TPO-RAs due to lack of response ([Ghanima 2019](#)). Novel, safe, and effective oral treatments to maintain platelet counts in this setting would be a significant therapeutic advantage. Thus, there remains a high unmet medical need for novel, safe, and effective oral therapies for ITP.

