3.2.4. Exploratory Endpoints

3.2.4.1. Blinded Treatment Period

- Proportion of participants able to achieve platelet counts $\geq 50,000/\mu\text{L}$ for 4 out of last 8 weeks of the 24-week treatment period
- Percentage of weeks with platelet count $\geq 50,000/\mu\text{L}$ OR between $\geq 30,000/\mu\text{L}$ and $< 50,000/\mu\text{L}$ and at least doubled from baseline over the 24-week blinded treatment period in the absence of rescue therapy
- Proportion of participants with complete response (defined as platelet count $\geq 100,000/\mu\text{L}$) on 2 consecutive visits at least 5 days apart and no bleeding or rescue ITP therapy use on and through these two visits.
- Proportion of participants with platelet count $\geq 50,000/\mu\text{L}$ on 2 consecutive visits at least 5 days apart and no rescue ITP therapy use on and through these two visits.
- Proportion of participants who have a platelet count that exceeds $250,000/\mu\text{L}$ or $450,000/\mu\text{L}$ (for participants on TPO-RAs)
- Change from baseline in ITP Bleeding Scale (IBLS) assessment at Week 13 and Week 25
- Change from baseline and change from Week 13 on the Fatigue (Item 10 of the ITP-PAQ; physical fatigue), Psychological, Fear, Social Activity, Women's Reproductive Health and Work domains of the ITP-PAQ in adult participants (≥ 18 years) at Week 25
- Change from baseline on the Psychological, Fear, Social Activity, Women's Reproductive Health and Work domains of the ITP-PAQ in adult participants (≥ 18 years) at Week 13
- Change from baseline in QOL as measured by the EuroQOL-5 Dimensions-5 Level (EuroQOL-5D-5L) in adult participants (≥ 18 years)

- Change from baseline in disease-related symptom severity as measured by the Patient Global Impression of Severity (PGIS) scale
- Change from baseline in disease-related fatigue severity as measured by the Patient Global Impression of [Fatigue] Severity (PGIS-Fatigue) scale
- Patient perception of disease-related symptom improvement as measured by the Patient Global Impression of Change (PGIC) scale
- PK parameters as assessed by population pharmacokinetic analysis
- BTK occupancy
- Changes from baseline in TPO levels, T-lymphocytes/ B-lymphocytes/natural killers (T/B/NK) counts, immunoglobulin (IgG, IgG1, IgG4, IgM, IgE) levels
- (Optional) Vaccine-specific IgG response during treatment

See [Appendix 10 \(Appendix 10.5\)](#) for China-specific requirements.

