9.3.2. Adverse Events

An AE is any untoward medical occurrence in a participant or clinical investigation participant administered a pharmaceutical product and which does not necessarily have to have a causal relationship with the intervention. An AE can therefore be any unfavorable and unintended sign (including an abnormal laboratory finding, for example), symptom, or disease temporally associated with the use of an IMP, whether or not considered related to the product. All AEs encountered during the clinical study will be reported in detail in the source documents and documented in the eCRF, from the date of participant consent throughout the follow-up visit. Pre-existing conditions that worsen during a study are to be reported as AEs, with the exception of expected variation in ITP disease activity itself.

Unexpected progression, signs, or symptoms of the disease under study (ITP) are not AEs and are not to be recorded on the AE page of the eCRF unless the event meets the definition of an SAE or is not consistent with the typical clinical course of the participant's disease as established by the participant's medical history. Worsening of the disease under study or other disease-related symptoms should be recorded as an AE only if the event meets the definition of an SAE or is not consistent with the typical clinical course of the disease.

Definitions:

The below guidelines should be followed when recording AEs:

- Medical terms: Whenever possible, use recognized medical terms when recording AEs on the AE eCRF. Do not use colloquialisms or abbreviations.
- Diagnosis: If known or suspected, record the diagnosis (except for eg, hypoglycemia) rather than component signs and symptoms on the AE eCRF and SAE form (eg, record congestive heart failure rather than dyspnea, rales, and cyanosis.) However, signs and symptoms that are considered unrelated to an encountered syndrome or disease should be recorded as individual AEs on the AE eCRF and SAE form.
- Death: Death is an outcome of an event. The event that resulted in the death should be recorded and reported on the AE eCRF and SAE form (except for sudden, unexplained death).

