- Surgical or diagnostic procedures: For medical or surgical procedures (eg, colonoscopy, biopsy), the medical condition that led to the procedure is an AE. Elective procedures(eg, vasectomy) planned hospitalizations, and procedures for treatment of conditions noted in the participant's medical history that have not worsened (eg, hernia repair) are not considered AEs.
- Chronic disease: In the case of disease (excluding disease under study) that is progressing by episodes (chronic disease), if the disease is known when the participant enters the study, only worsening (increased frequency or intensity of the episodes or attacks) will be documented as an AE. If the disease is detected during the study, and if repeated episodes enable diagnosis of a chronic disease, the episodes will be grouped together in the eCRF, and the diagnosis will be clearly described.

- Underlying disease conditions: Unchanged (stable), chronic conditions, or those related to the underlying disease that are consistent with the disease's natural progression are not AEs and are not to be recorded on the AE page of the eCRF. These conditions are considered part of the participant's medical history and must be adequately documented on the appropriate page of the eCRF. Day-to-day fluctuations of pre-existing disease should not be recorded as an AE on the AE eCRF.
- Disease under study (ITP): Unexpected progression, signs, or symptoms of the disease under study are not AEs and are not to be recorded on the AE page of the eCRF unless the event meets the definition of an SAE or is not consistent with the typical clinical course of the participant's disease as established by the participant's medical history. Worsening of the disease under study or other disease-related symptoms should be recorded as an AE only if the event meets the definition of an SAE or is not consistent with the typical clinical course of the disease.
- Laboratory abnormalities: An isolated, out-of-range laboratory result in the absence of any associated, clinical finding may or may not be considered an AE; the Investigator's evaluation should be based on a consideration of the overall clinical context.

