- New conditions detected or diagnosed after study intervention administration even though it may have been present before the start of the study.
- Signs, symptoms, or the clinical sequelae of a suspected drug-drug interaction.
- Signs, symptoms, or the clinical sequelae of a suspected overdose of either study intervention or a concomitant medication.
- Signs, symptoms, or the clinical sequelae of any medication errors, misuse, and abuse with the IMP. An abuse corresponds to the persistent or sporadic, intentional excessive use of a medicinal product, which is accompanied by harmful physical or psychological effects, ie, intentional non-therapeutic use of a medicinal product by a participant for a perceived reward or desired non-therapeutic effect including, but not limited to, “getting high” (euphoria).
- “Lack of efficacy” or “failure of expected pharmacological action” per se will not be reported as an AE or SAE. Such instances will be captured in the efficacy assessments. However, the signs, symptoms, and/or clinical sequelae resulting from lack of efficacy will be reported as AE or SAE if they fulfill the definition of an AE or SAE.
- The signs, symptoms, and/or clinical sequelae resulting from lack of efficacy will be reported as AE or SAE if they fulfill the definition of an AE or SAE. Also, “lack of efficacy” or “failure of expected pharmacological action” also constitutes an AE or SAE.

Events NOT meeting the AE definition

- Any clinically significant abnormal laboratory findings or other abnormal safety assessments which are associated with the underlying disease, unless judged by the Investigator to be more severe than expected for the participant’s condition.
- The disease/disorder being studied or expected progression, signs, or symptoms of the disease/disorder being studied, unless more severe than expected for the participant’s condition.
- Medical or surgical procedure (eg, endoscopy, appendectomy): the condition that leads to the procedure is the AE.
- Situations in which an untoward medical occurrence did not occur (social and/or convenience admission to a hospital).
- Anticipated day-to-day fluctuations of pre-existing disease(s) or condition(s) present or detected at the start of the study that do not worsen.

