#### 3.7.3.1 ITP Bleeding Scale (IBLS)

The ITP IBLS (5) is a bleeding assessment system comprising 11 (10 for male) site-specific grades from 0 (none) to 2 (marked bleeding) assessed at nine anatomical sites by history over the previous period (Hx). In addition, two of these sites, skin and oral, were also assessed by physical examination (PE). The ‘worst ever’ bleeding experienced at each site was graded using the same system. Refer to [Section 5.5](#) for an example of the copyrighted scale.

The IBLS were assessed at each visit with a 1-week recall period for Hx. For each participant, an IBLS score at each visit will be calculated by taking the average across 11 items (10 for male and postmenopausal female) at 9 sites (8 for male and postmenopausal female). Specifically,

- IBLS score will be calculated only if it is assessed for  $\geq 1$  anatomic sites at a visit. “Not done” is handled the same as “None” with grade 0 ([Section 5.5.1](#)).
- IBLS score will not be calculated if it is not assessed at any anatomic sites at a visit.

For each patient, a mean IBLS score will also be calculated by taking the average across post-baseline visits during the double-blind on-treatment period.

Frequency and severity of bleeding according to IBLS will be summarized at each visit including IBLS score defined above. Mean IBLS score will also be descriptively summarized. In addition, change from baseline in IBLS score will be compared between rilzabrutinib and placebo in the adult participants at Week 25 ([Section 3.3.1.2.5](#)) and Week 13 ([Section 3.3.1.4.1](#)).

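### The no-bleeding part of complete response is read from the AE page alone, where typical non-serious ITP bleeding is not to be recorded, so bleeding graded on the IBLS can go uncounted

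*SAP*

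**What the plan says.** Protocol 3.2.4.1 lists complete response as an exploratory endpoint: a platelet count of at least 100,000/µL at two consecutive visits at least 5 days apart, with "no bleeding or rescue ITP therapy use on and through these two visits". It gives no data source and no grade or seriousness threshold for bleeding. Protocol 3.2.4.2 repeats the endpoint for the open-label and long-term extension periods.

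SAP 3.4.1 turns the bleeding condition into "bleeding events identified by SMQ = Haemorrhages via broad and narrow search in eCRF" Adverse Events. The phrase is introduced by ie, so it defines the condition and does not merely illustrate it.

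Protocol 9.3.2 restricts that page. Pre-existing conditions that worsen are AEs, "with the exception of expected variation in ITP disease activity itself". Of the signs and symptoms of ITP itself, it says that they "are not AEs and are not to be recorded on the AE page of the eCRF unless the event meets the definition of an SAE"; the only other exception is for an event out of keeping with the participant's usual course. On worsening, the same section says: "Worsening of the disease under study or other disease-related symptoms should be recorded as an AE only if the event meets the definition". The condition there is again seriousness or an atypical course. Appendix 12.1 lists among non-AEs the expected progression, "signs, or symptoms of the disease/disorder being studied, unless more severe than expected".

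SAP 3.7.3.1 describes the other bleeding source: "The IBLS were assessed at each visit with a 1-week recall period for Hx". The SAP uses the IBLS for its own summaries and for change-from-baseline comparisons. Neither SAP 3.4.1 nor 3.7.3.1 brings it into complete response.

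**The concern.** Bleeding is part of the disease: Protocol 2.1 describes ITP as thrombocytopenia with a "predisposition to bleeding associated with morbidity and mortality". A site that follows Protocol 9.3.2 will leave typical, non-serious bruising, petechiae or gum bleeding off the AE page. An empty AE page therefore does not show that there was no bleeding. The IBLS grades these events and is already collected.

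What is at stake is whether a descriptive rate means what its label says. The clinical study report could show IBLS bleeding for a participant at a visit and count the same participant, at the same visit, as a complete responder without bleeding. The issue applies in the blinded, open-label and extension periods.

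**Working it through.** The plan gives no figure to reproduce here. The check sets the rules side by side, then counts how far the IBLS could reach.

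**1. Can the rules produce the mismatch?** Take a participant with two consecutive counts of at least 100,000/µL at least 5 days apart, no rescue in the 4 weeks before or through the two visits, and an IBLS item graded 1 or 2 at one of those visits. Suppose the bleeding is non-serious and usual for that participant.

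- Platelet criterion (SAP 3.4.1): met.
- Rescue criterion (SAP 3.4.1): met.
- AE page (Protocol 9.3.2): no entry is due, so the haemorrhage search finds nothing and the bleeding criterion is met.
- IBLS (SAP 3.7.3.1): bleeding is recorded, but SAP 3.4.1 does not look there.

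Result: a complete responder, with the plan followed exactly.

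**2. Direction.** A participant responds if at least one visit pair qualifies. Adding an IBLS condition to the AE condition can remove pairs but cannot add any. The responders under the combined rule are therefore a subset of those under the AE-only rule, so the AE-only rate is equal or higher.

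**3. Reach of the IBLS in the blinded period.**

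Inputs:
- Response may occur at any time from Week 2 to Week 25 (SAP 3.4.1).
- Clinic visits with an IBLS fall at Weeks 5, 9, 13, 17, 21 and 25 (Protocol Tables 1 and 2).
- Weekly lab visits between clinic visits are for platelet counts only (Protocol Table 1, footnote u).

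Consecutive pairs (w, w+1) run from w = 2 to w = 24:

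| Pair type | Pairs | Count |
|---|---|---|
| Second visit has an IBLS | 4–5, 8–9, 12–13, 16–17, 20–21, 24–25 | 6 |
| Only the first visit has an IBLS | 5–6, 9–10, 13–14, 17–18, 21–22 | 5 |
| Neither visit has an IBLS | the rest | 23 − 6 − 5 = 12 |

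An IBLS falls on 6 + 5 = 11 of 23 pairs (11/23 = 48%). In 6 of 23 (26%) the one-week recall spans the interval at the nominal 7-day spacing. In the other 5, the history items describe the week before the first qualifying visit, which lies outside the window, and only the physical-examination items (skin and oral) bear on it.

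**4. Long-term extension.** Every scheduled clinic visit has an IBLS (Protocol Table 3). In the first year visits are 28 days apart, so one-week recall covers 7/28 = 25% of the interval.

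**5. What cannot be computed.** The number of participants reclassified depends on how often typical, non-serious bleeding occurs at counts of at least 100,000/µL and how often sites enter it as an AE anyway. The documents give neither. The 48% describes schedule overlap, not misclassification.

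**The case against.** The strongest case against is that the AE page need not be close to empty. Bleeding TEAEs are a safety endpoint (Protocol 3.2.3.2), and the SAP tabulates bleeding TEAEs of Grade 2 or higher (SAP 3.6.2). Bleeding is also a BTK-inhibitor class effect that the sponsor says it will monitor closely (Protocol 2.7.1.1 and 2.7.3). Entry required an average count below 30,000/µL, so an investigator could reasonably judge bleeding at 100,000/µL or more to be atypical and record it. Appendix 12.1 also asks for signs and symptoms of lack of efficacy to be reported when they meet the AE definition. All of this stands, and it makes the effect conditional: IBLS-graded bleeding is missed only when the site did not also enter an AE.

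The protocol names no source for the bleeding condition, so the SAP fills a gap and does not contradict the protocol. That also stands. SAP Table 11 records that the IBLS was considered not validated. This was given as a reason when Item 10 of the ITP-PAQ was introduced as a key secondary endpoint, and the IBLS change score remains a key secondary endpoint for the EU and UK. Noting whether bleeding was seen at a visit does not depend on validation of the averaged score.

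A reader might go further and infer that such participants will be scored complete responders, that the bleeding condition has almost no effect, or that the comparison between arms is biased. The documents support none of these. They give no rate for the missed events and nothing to suggest that AE-page recording differs by arm.

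**Conclusion.** The point holds in a limited form. As written, SAP 3.4.1 can count a participant with typical, non-serious, IBLS-graded bleeding as a complete responder without bleeding, because its only source is a page from which Protocol 9.3.2 excludes such bleeding. Relative to a rule that also uses the IBLS, the reported rate is equal or higher by an amount that cannot be estimated from the documents.

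The conclusion assumes that sites follow Protocol 9.3.2 and that some bleeding at qualifying counts is judged usual for the participant. Severity is low: SAP 3.4.2 makes exploratory analyses mainly descriptive with no testing, and the endpoint is outside the fixed-sequence procedure of SAP 3.5. No confirmatory result depends on it.

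**What to change.** In SAP 3.4.1, define the no-bleeding condition as both of the following:

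- (a) no haemorrhage-SMQ AE starting or ongoing from the first to the second qualifying visit; and
- (b) where an IBLS was done, no physical-examination item graded 1 or 2 at either visit or between them, and no history item graded 1 or 2 at an IBLS whose one-week recall falls within the window. That means the second or an intervening visit, not the first.

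For this purpose, treat Not done as not assessed. SAP 3.7.3.1 scores it as grade 0, which would let an unassessed site count as free of bleeding. Report how many qualifying pairs had an IBLS, and how many had one with recall over the interval. Present the AE-only rate alongside, labelled as no bleeding AE.

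The cost is SAP wording and a merge of data already collected, with no new assessments. The rate may fall. Pairs without an IBLS (12 of the 23 possible blinded pairs) remain AE-based, so a participant rejected on one pair could still qualify on another that has no IBLS. Reporting both versions with the coverage counts lets a reader see this.
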